1.0 Objectives

In this multistep study, we will build on our prior efforts¹ to develop consensus on surveillance mammography and follow-up for breast cancer survivors who are age ≥ 75 by further developing expert-panel recommendations, examining clinician and patient attitudes towards these recommendations, and testing a strategy for communication of expert recommendations on mammography cessation through direct engagement of specialists, primary care clinicians (PCs), and patients. Specifically, we will work to reduce overscreening of older patients through the following aims:

- 1.1 Develop a communication tool that summarizes recommendations for clinicians and patients for surveillance mammography and follow-up care for breast cancer survivors age ≥ 75 . This will build off the work of a multidisciplinary expert panel which will come together for a meeting to develop draft recommendations (OHRS exempt protocol #18-526).
 - Interview up to 30 patients through telephone-based patient interviews and focus groups and interview oncologists and primary care providers (PCs) through 4-6 focus groups to learn their perceptions and thoughts about when to stop surveillance mammography, how to thoughtfully incorporate life expectancy into decision-making, how to communicate the benefits/risks of surveillance mammography, obtain feedback on the communication tool, and to explore optimal strategies for integrated and unified care between disciplines
 - Perform cognitive testing of the communication tool in up to 10 Dana-Farber breast cancer patients and further refine it for Aim 1.2
- 1.2 Test the surveillance mammography communication tool with older breast cancer survivors and their oncology clinicians
 - In a pre-post intervention study, examine the effect of the communication tool among 45 breast cancer survivors age ≥ 75 years (with low risk of in-breast recurrences) seen by oncologists on women's intentions for and knowledge of the pros and cons of surveillance mammography.

We hypothesize that our communication tool will lead to fewer women intending to receive surveillance mammography in the next year and women having more knowledge of the benefits and risks of surveillance mammography.

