If the clinician agrees, the CRC will send information and what will be used for verbal consent (Appendix F) to the patient with an opt-out number and email followed by a phone call (to those who do not opt out) to explain the study's purpose and obtain verbal consent for participation. The CRC will share a blank communication tool to the patient with the 'pre'survey to be filled out before the visit (clinic visit can be virtual or in person), and notify the clinician when a patient enrolls. This can be sent to the patient by mail or email in advance of their virtual/in person clinic visit. If the patient prefers the materials to be given to them in person, the CRC will arrange to meet the patient 30 minutes before their scheduled clinic visit. If the clinic visit is virtual, the CRC can call the patient anytime ahead of the provider visit to review the materials. The study team will be utilizing standard clinical workflows and may involve virtual substitution of office visits such as the use of Zoom Video Communications application. Although in-person office visits are preferred on site, virtual visits via Zoom conferences, which are HIPPA compliant and protected, can provide a safer and efficient alternative for patients.

Visit Day. The day before the clinic visit (virtual or in-person), the CRC will call or email the patient to remind them to fill out the 'pre'-survey and send it to the study team. We will also remind the clinician that the patient is coming/being seen virtually and will email or hand-deliver a blank communication tool before the visit so they are aware it may be discussed. The CRC may meet the patient in the waiting room or communicate by phone/email before their appointment to collect the 'pre' survey (if not already received via email/mail) A copy of the verbal consent can also be given in person or via email/mail if not already done ahead of this visit. Clinicians will be reminded to incorporate the communication tool in a way that feels comfortable to them to facilitate routine practice but without specific instructions. After the visit, the CRC

PROTOCOL TITLE:

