APPENDIX B

Updated (May 2020) Communication Tool
(adapted and revised from [name] prior and ongoing decision aid work)
[Schonberg, M.A. et al JAMA Intern Med, 2014. 174(3):417-424]

MAMMOGRAPHY FOR BREAST CANCER SURVIVORS AGE 75+

Are mammograms still right for me?

The benefits and risks of mammograms change as women grow older.

For breast cancer survivors who are 75 years of age or older, mammograms may be less useful than before, and often women can safely stop

getting them. Our risk of breast cancer and other health conditions changes as we age.

Many women are glad to stop mammograms, which can be stressful, painful, or result in more tests like ultrasound or biopsy that, in the end, do not find cancer.

Others do not feel comfortable stopping, especially if they have been told for most of their lives that they should have a mammogram every year.

Whether mammograms will continue to be helpful for you depends on your breast cancer risk, your health in general, and what's important to you.

Accurate, expert information

Many breast cancer survivors

fear that their risk of another breast cancer is higher than other women, but this is often not the case. It's important to make your decision with information that is accurate and trustworthy.

This guide was developed by national cancer experts and is based on review of hundreds of available clinical trials and studies.

Talk to your health care provider

This guide can help you understand:

- Your breast cancer risk
- Your health in general
- What's important to you

Your health care provider can answer your questions and help decide what's right for you.

1. Understanding your breast cancer risk

Understanding your breast cancer risk can help you make the best decision about future mammograms.

Most older breast cancer survivors have a similar risk of future breast cancer as other older women who did not have breast cancer. Many women are surprised to learn this.

[figure not shown]
If you received hormone therapy for your breast cancer, your risk is much lower risk than other women.

If your risk is the same as or lower than other older women who did not have breast cancer, you may want to consider stopping mammograms.

For women whose risk is higher than average because of their tumor type, treatment, or family history, mammograms may continue to be useful.

The charts on the next page show show the average risk of future breast cancer among breast cancer survivors.

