Not at all difficult **0** | A little to very difficult, can't do it, don't do it, or can only do it with cane or walker **2** |

What is your cigarette use?

Never smoked or smoked less than 100 cigarettes in your life **0** | Former smoker **2** | Current smoker **4** |

How many times did you stay in the hospital overnight during the past year?

None **0** | Once **1** | Twice or more **3** |

Add up your points for questions 1-10

Based on your answers about your general health:

If your score was between 0-6, a mammogram may still be useful.

If your score was 7 or more, other health issues may be of more concern than your breast cancer risk, and a mammogram may not be useful.

3. What's important to you?

There's no right or wrong decision about mammograms—just the decision that's right for you. Here are some of the key reasons to have mammograms (benefits) or stop them (harms). Please check the reasons that feel important to you.

Reasons to have mammograms

- I'm more at risk than other women because of my cancer sub-type, treatment, or family history.
- I believe that continuing to have mammograms will help me stay healthy.
- Having mammograms helps me feel I am taking care of myself.
- I am worried about cancer returning to my affected breast.
- I'm worried about breast cancer in my unaffected breast.

Reasons to stop having mammograms

- My risk is low because of my cancer sub-type, treatment, and family history.
- I am more worried about other health issues.
- I'd rather rely on clinical breast exams by my health care provider.
- I do not want to find breast cancer that won't cause a problems in my lifetime.
- If I found a new breast cancer, I don't think I would want to have treatment for it.
- It is stressful when a mammogram requires more tests that then do not find cancer.
- Mammograms are sometimes painful.
- I would like to avoid the small amount of radiation from mammograms over time

4. Discuss and decide with your doctor

Talk with your health care team to help decide whether continuing to have mammograms is right for you. Important things to discuss are:

- The possible benefits or harms of mammograms based on your cancer sub-type, treatment, and family history
- Your risk for a new breast cancer or a cancer coming back in your breast
- Your general health
- What's important to you

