The next questions are questions and are the same questions we asked you on your baseline survey. Please state whether each of the following statements is true or false (your best guess is fine).

21. Among women aged 75 or older, who is more likely to die from breast cancer?

- Women who get mammograms
- Women who do NOT get mammograms
- There is almost no difference
- Don't know

22. The benefit of getting a mammogram is finding and treating a breast cancer when it is small and can be treated with only minor surgery.

PROTOCOL TITLE:

- True False

23. Getting a mammogram will prevent me from getting breast cancer.

- True False

24. Most women who have an abnormal mammogram have breast cancer.

- True False

25. Women aged 75 or older have a higher chance of getting breast cancer than younger women.

- True False

26. More women aged 75 or older die of heart disease than breast cancer.

- True False

27. Your other health problems should affect whether or not you get a mammogram.

- True False

28. Some breast cancers found by a mammogram would never have shown up or caused problems in a woman's lifetime.

- True False

29. Most women aged 75 or older with breast cancer are treated with chemotherapy.

- True False

30. Some breast cancers are not detected by mammograms.

- True False

The next questions are about the communication tool that we provided you before your clinic visit

Did it...

31. Help you recognize that a decision needs to be made about whether or not to get a mammogram?

- A great deal Quite a bit Somewhat A little Not at all

32. Prepare you to make a better decision about whether or not to get a mammogram?

- A great deal Quite a bit Somewhat A little Not at all

33. Help you think about the pros and cons of getting a mammogram?

- A great deal Quite a bit Somewhat A little Not at all

34. Help you think about which pros and cons about getting a mammogram are most important to you?

- A great deal Quite a bit Somewhat A little Not at all

PROTOCOL TITLE:

35. Help you know that the decision whether or not to get a mammogram depends on what matters most to you?

-
- A great deal Quite a bit Somewhat A little Not at all

36. Help you organize your own thoughts about the decision whether or not to get a mammogram?

-
- A great deal Quite a bit Somewhat A little Not at all

37. Help you think about how involved you want to be in this decision?

-
- A great deal Quite a bit Somewhat A little Not at all

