Per our medical record review, it seems that *[name] is aged 75 or older, had breast conservation, and is in long-term follow-up care for her breast cancer. She is likely eligible for protocol 19-001.* As you may know, this is survey-based study where patients will be given an information tool to discuss mammography with you that can be used as you like and per your discretion. Patients will be surveyed before and after your visit on their mammography decisions and how the information tool may have helped/not helped them make decisions. Participants will receive \$40 for their time. ***This cohort is purely survey-based and there is no therapeutic component to the study.***

If we do not hear from you within 2 business days, we will assume permission to initiate contact with the patient. We will mail your patient an introduction to the study and then call them a week later to assess their interest. If this patient is interested in participating, we will be responsible for consenting her and for all study procedures. **We will survey you at the end of the patient encounter via email and at the end of the study, you will receive a \$40 amazon gift card in appreciation of your time.**

Thank you for your assistance and support of this study. Please feel free to contact us if you have any questions.

Sincerely,

[name], MPH

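### In Aim 1.2 the pre survey reaches the patient together with the tool and is timed only against the visit, so the baseline may be answered after the tool has been read

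*Protocol*

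**What the plan says.** Protocol section 1.0 sets the purpose of Aim 1.2: "In a pre-post intervention study, examine the effect of the communication tool among 45 breast cancer survivors". There is no control group.

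Section 5.3 sets the timing of tool and survey:

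- **Delivery.** "The CRC will share a blank communication tool to the patient with the 'pre'survey to be filled out before the visit". Both may go by mail or email with no stated lead time, or be handed over half an hour ahead of the appointment.
- **Virtual visits.** "If the clinic visit is virtual, the CRC can call the patient anytime ahead of the provider visit to review the materials". There is no condition that the survey is already done.
- **Reminder.** The patient is prompted about the survey on the day before the visit, when a mailed or emailed tool may already be with her.
- **Collection.** "The CRC may meet the patient in the waiting room or communicate by phone/email before their appointment to collect the 'pre' survey".

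Other parts of the documents anchor the surveys to the visit and not to the tool. Appendix H tells clinicians: "Patients will be surveyed before and after your visit on their mammography decisions". The SAP labels the surveys pre-visit and post-visit. The post-visit patient questionnaire in Appendix D introduces its tool items with "The next questions are about the communication tool that we provided you before your clinic visit".

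The visible part of the pre questionnaire has no instruction to answer before opening the tool.

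**The concern.** In an uncontrolled pre-post design the baseline stands in for the missing comparison group, so it has to be taken before exposure. Here the tool and the baseline survey share one window that ends at the visit. The tool is meant to be read in that window, because the post survey asks whether it prepared the patient for the discussion.

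For a woman who reads first, the contrast measures the visit alone, whereas for one who answers first it measures tool plus visit. The analysis pools the two without knowing who is who. The contrast carries change in intention (a primary outcome in section 8.5), knowledge and decisional conflict. The SAP uses the decisional-conflict change to help design a future trial, so a distorted estimate would carry forward into that design.

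**Working it through.** The plan states no figure on this point, so there is nothing to reproduce. The check has three parts.

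**1. Is an order stated anywhere?** I looked at the visible text on Aim 1.2 timing: sections 1.0, 5.3, 8.4, 8.5 and 9.3, the Appendix D questionnaires, Appendix H and the SAP. None of it puts the survey before the tool, withholds the tool until the survey is returned, or records which came first. In the in-person route staff could control the order, but no order is given. Aim 1.1 differs: its interview script in Appendix C has the patient keep the packet sealed until the interviewer says to open it.

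**2. Does the tool address what the baseline asks?** Appendix B set against the pre survey in Appendix D:

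| Pre survey content | Related tool text | Count |
|---|---|---|
| Intention (item 1) | "mammograms may be less useful than before, and often women can safely stop" | the item itself |
| Knowledge (items 18 to 27) | Item 24, on other health problems: "other health issues may be of more concern than your breast cancer risk, and a mammogram may not be useful". Item 25, on cancers that would never cause trouble: implied by a section 3 checklist reason | 2/10 = 20% |
| Knowledge, wider count | Item 21 added: the tool mentions further tests that find no cancer | 3/10 = 30% |
| Decisional conflict (items 2 to 17) | Items 3 to 7: section 3 sets out benefits, harms and personal priorities | 5/16 = 31% |

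Item 24 is addressed plainly and item 25 only by implication. The tool's risk charts are missing from the text available to me, so the knowledge count may be low.

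**3. What would prior reading do to the contrast?** Let f be the share who read first, R the mean effect of reading and V the mean effect of the visit, taken as additive. All three are assumptions.

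- Intended change: R + V
- Observed change: V + (1 − f)R
- Bias: [V + (1 − f)R] − (R + V) = −fR
- Share lost, if R and V have the same sign: fR/(R + V)

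| Case | f | Share lost |
|---|---|---|
| R = V | 0.25 | 0.25 × 1/2 = 12.5% |
| R = V | 0.5 | 0.5 × 1/2 = 25% |
| R = V | 1 | 1 × 1/2 = 50% |
| V = 2R | 0.5 | 0.5 × 1/3 = 16.7% |
| R = 2V | 0.5 | 0.5 × 2/3 = 33.3% |

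If nobody reads first, the loss is zero.

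**Scale against n = 45.** The documents give no alpha, power or effect size for Aim 1.2. Assume a paired normal approximation, two-sided alpha 0.05 and 80% power. The detectable standardised change is (1.960 + 0.842)/√45 = 0.418. If a share s of that change is lost, power is about Φ((1 − s) × 2.802 − 1.960) plus a negligible opposite tail, and the n that restores 80% power is 45/(1 − s)².

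| s | Power | n for 80% power |
|---|---|---|
| 0.25 | 56% | 80 |
| 0.50 | 29% | 180 |

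These rows show sensitivity only and do not estimate what happened.

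**The case against.** The strongest reply is that the place most likely to hold an order instruction cannot be seen. Patients are briefed through Appendix F and a consent call, and neither the Appendix F text nor pre items 31 to 36 was available to this review. The instrument is also headed as a baseline, and a call about the materials could concern the survey only. This limits the claim to what the visible text permits, and nothing shows that any patient did read first. It does not supply an order for section 5.3, which is what staff follow.

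Second, f, R and V are invented, and the direction is not secured. Section 1.0 hypothesises about intention and knowledge but not decisional conflict, and clinicians use the tool at their own discretion, so the visit could push against the reading effect. This stands. The bias −fR holds under additivity whatever the signs, but loss toward zero is a conditional statement, and for decisional conflict no direction can be claimed.

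Third, this is a small pilot meant to give preliminary data, and the acceptability and feasibility outcome uses no pre-post contrast. That is correct and limits the reach, but intention is also a primary outcome.

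Fourth, the SAP is written in the past tense, so resequencing may come too late. That affects which remedies remain, not whether the gap exists.

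**Conclusion.** The concern holds. As visibly written, section 5.3 allows the only comparator in Aim 1.2 to be collected after exposure to the intervention it is meant to precede, and it does not record when that happens. Change in intention, knowledge and decisional conflict are affected; acceptability and feasibility are not.

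The size is unknown. The illustrations run from no loss to half of the change when reading and visit effects are equal and in the same direction, and they rest on assumed values and additivity. Confidence is moderate because Appendix F and part of the pre survey were not seen. The point should be fixed, or disclosed if data collection has ended.

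**What to change.** - **Order.** State in section 5.3 and at the top of the pre survey that the survey is completed before the tool is opened, and confirm that Appendix F says the same.
- **Delivery.** In REDCap, release the tool when the survey is submitted. For mail or hand delivery, put the tool in a sealed envelope in the same packet, as Aim 1.1 already does.
- **Coordinator contact.** Place any review of the tool after the survey.
- **Data.** Add one field recording whether the tool was read before the survey, and also report the pre-post change in patients whose baseline preceded exposure. That subgroup will be small and self-reported, so treat it as a sensitivity analysis.

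If collection is complete, check Appendix F and use survey dates, contact tracking sheets and REDCap records to narrow the exposure window. Because tool and survey arrive together, these records cannot show which came first. The report should therefore say that the baseline may follow exposure, and the sequencing should be carried into the future trial.

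The cost is two sentences, a REDCap setting, envelopes and one field. A patient who completes the 60-item survey late, or meets the coordinator just before the visit, has less time with the tool. That could slightly affect the preparation items (post 31 to 40) and the usefulness outcome. Sending the sealed packet early limits this.
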